8.2.2 Definition of Derived Variables

8.2.2.1 Patient-reported Assessments Captured in eDiary

CeD PRO Domain Scores

The CeD PRO is captured daily in the eDiary after the last meal of the day before the subject goes to bed. It includes 9 items asking participants about the severity of celiac disease symptoms they may experience each day. Participants are asked to rate their symptom severity on an 11-point (0 to 10) scale; from "not experiencing the symptom" to "the worst possible symptom experience". Symptoms include abdominal cramping, abdominal pain, bloating, gas, diarrhea, loose stool, nausea, headache, and tiredness (Figure 2).

[figure not shown]
Analyses will be performed on all individual domain scores and weekly worst symptom domain scores in the GI symptom domains (Abdominal Symptoms and Diarrhea/Loose Stool domains) and Total GI score (Abdominal Symptoms Domain + Diarrhea/Loose Stool Domain + Nausea item). The Total GI score will be assessed with and without inclusion of the Nausea item.

Daily mean domain score is calculated as sum of daily item scores for all items within a domain divided by number of items in the domain.

Weekly domain scores are based on analysis visit windows (defined below) and calculated as the sum of non-missing daily mean domain scores divided by the number of non-missing scores of a given week. A weekly score is calculated if there are at least 4 non-missing daily scores available. Weekly mean total GI score is calculated as the sum of weekly mean Abdominal Symptoms domain score, Diarrhea and Loose Stools domain score, and Nausea item score divided by 3. The weekly mean total GI domain score without the Nausea item, is calculated as the sum of weekly mean Abdominal Symptoms domain score, Diarrhea and Loose Stools domain score divided by 2. If any of the weekly domains are missing, the total score will be calculated as the average over the remainder non-missing weekly domain scores.

Figure 2. Symptom Domains in the Celiac Disease Patient-Reported Outcome Questionnaire

CeD PRO Symptomatic Days

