Symptomatic days will be assessed in terms of the Abdominal Domain, Diarrhea and Loose Stool Domain, and Total GI score of the CeD PRO. A given day is defined as a symptomatic day if any of the domain scores is >0. A day is considered asymptomatic if all of these scores are 0. The number of symptomatic days and asymptomatic days will be derived by month (including baseline) [based on month-based visit windows defined below] and total during the double-blind treatment period (through Week 24).

Weekly Worst Symptom Domain Score in CeD PRO

Weekly worst symptom domain scores will be derived separately for each of the following three domains: 1) Abdominal Domain score, 2) Diarrhea and Loose Stool Domain score, and 3) Total GI score by selecting the worst daily score for all items within each domain for a given week (based on analysis visit windows defined below) and averaging these scores.

BSFS Stools of Type 6 or 7

The BSFS is a pictorial aid to help subjects identify the shape and consistency of their stools during the study (Riegler et al, 2001). The subject will be asked to record the number of stools that have a consistency of Type 6 or 7 (loose stool or entirely liquid) at bedtime daily in the eDiary. On the days in which the subject experiences no such stool (BSFS Type 6 or 7), the subject should record 0 in the eDiary instead of leaving it blank. The sum of weekly stool frequency (sum of the previous 7 days) through Week 24 for stools of BSFS Type 6 or 7 will be calculated, based on the analysis visit windows (defined below). In case of multiple records for stool in one day the latest record in time will be considered.

Baseline Value for Patient-Reported Assessments captured in eDiary

In general, the last non-missing value prior to the first dose of double-blind treatment will be used as the baseline value.

For patient-reported assessments captured in the eDiary, the following definitions of baseline in Table 2 will be used:

Table 2. Definition of Baseline for Patient-Reported Assessments Captured in eDiary

Assessment	Baseline Definition				
CeD PRO (Abdominal domain and other weekly domain scores)	Average of scores from 7 days prior to randomization (e.g., last week of placebo run-in).				
BSFS	Sum of Type 6 or 7 stool experienced over the 7 days prior to the date of first dose of double-blind treatment.				
PGIC/PGIS	Most recent assessment prior to the first administration of double-blind treatment.				

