8.6.3 Other Efficacy Variable(s)

All other efficacy variables will be analyzed on mITT analysis set, if not specified otherwise. Tabulation by subgroups, where noted, is referring to the subgroups as specified for the subgroup analysis of primary and secondary efficacy variables.

CeD PRO non-GI Domain Scores (Headache and Tiredness Items)

Change from baseline through Week 24 in the CeD PRO non-GI domain scores (headache and tiredness items) will be tabulated by treatment group and by time point, both overall and by subgroups.

Mean change from baseline by treatment group and time point will be plotted, both overall and by subgroups.

CeD PRO Nausea Domain Scores

Change from baseline through Week 24 in the CeD PRO Nausea domain score will be tabulated by treatment group and time point, both overall and by subgroups.

Mean change from baseline by treatment group and time point will be plotted, both overall and by subgroups.

CeD PRO Symptomatic and Asymptomatic Days

Symptomatic (Score of greater than 0) and asymptomatic (Score of 0) days will be assessed in terms of the Abdominal Symptoms domain, Diarrhea and Loose Stool Domain, and Total GI score of the CeD PRO in a binary way.

In order to make the post-baseline number of symptomatic and asymptomatic days comparable with the baseline, the ratio of the total numbers to the overall number of days and the ratio of monthly numbers to the total number of days at each month through Week 24 will be summarized for each domain. Other cut off points for symptomatic scores including Score of ≥ 2 or Score of ≥ 3 in the domain scores will be evaluated.

MMRM analysis will be performed to assess changes from baseline through Week 24 on monthly totals of symptomatic days for each domain, with treatment, week, and week by treatment as fixed effects, the continuous baseline Abdominal Symptoms domain score and VH:CD ratio as covariates, and subject as a random effect. The model will be similar to that of the primary model.

Percent Change from Baseline in CeD PRO Domains

Percent change from baseline through Week 24 in the Abdominal Symptoms domain, the Diarrhea and Loose Stool domain, and the Total GI score of the CeD PRO will be summarized by treatment group and time point.

Proportion of Subjects Who Reach 30% and 50% Reduction in CeD PRO Domains

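### SAP 8.2.2.1 defines one composite symptomatic day, but SAP 8.6.3 analyzes symptomatic days domain by domain; programmed as derived, the three domain analyses would carry the same data

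*SAP*

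**What the plan says.** **SAP 8.2.2.1, CeD PRO Symptomatic Days.** The paragraph opens by naming three scores: "Symptomatic days will be assessed in terms of the Abdominal Domain, Diarrhea and Loose Stool Domain, and Total GI score of the CeD PRO". It then gives one rule for the day: "A given day is defined as a symptomatic day if any of the domain scores is >0", with the complement "A day is considered asymptomatic if all of these scores are 0". Day counts are derived by month, baseline included, and in total through Week 24.

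**SAP 8.2.2.1, CeD PRO Domain Scores.** The composition of Total GI is given in brackets: "Total GI score (Abdominal Symptoms Domain + Diarrhea/Loose Stool Domain + Nausea item". A daily domain score is the mean of its items. For Total GI only a weekly formula is given (three components, divided by 3).

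**SAP 8.6.3, CeD PRO Symptomatic and Asymptomatic Days.** Here the classification follows the score in question: "Symptomatic (Score of greater than 0) and asymptomatic (Score of 0) days will be assessed in terms of the Abdominal Symptoms domain", and likewise for the Diarrhea and Loose Stool domain and the Total GI score. Ratios of symptomatic days are summarized for each domain, and "MMRM analysis will be performed to assess changes from baseline through Week 24 on monthly totals of symptomatic days for each domain". The section also plans higher thresholds ("Other cut off points for symptomatic scores including Score of" 2 or more, or 3 or more).

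**The concern.** One section produces a single flag per subject-day and the other needs three. The sentence on asymptomatic days, which requires every score to be 0, closes off a domain-by-domain reading of the rule in 8.2.2.1. That section falls under the heading for derived variables, so a programmer could reasonably follow it.

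Two things are at stake. First, three MMRMs labeled Abdominal, Diarrhea and Loose Stool, and Total GI would return one result three times. SAP section 7 says that endpoints and dose for confirmatory studies will be chosen on the totality of evidence, and three matching results could be misread as agreement across domains. Second, the analysis labeled Diarrhea and Loose Stool would count days on which the subject had no diarrhea or loose stool.

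**Working it through.** The documents state no figure for symptomatic days, so there is none to reproduce.

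**Inputs.** Four Abdominal items (pain, cramping, bloating, gas; Protocol 8.2.1), two Diarrhea and Loose Stool items, one nausea item, each scored 0 to 10 (SAP 8.2.2.1). Diary days are taken as complete.

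**1. Identity.** Write A, D and N for the daily Abdominal, Diarrhea and Loose Stool, and nausea scores, all at least 0. Total GI is their sum or their mean, so Total GI > 0 exactly when A > 0 or D > 0 or N > 0. The 8.2.2.1 rule is A > 0 or D > 0 or Total GI > 0. The first two conditions each imply the third, so the rule reduces to Total GI > 0.

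**2. Enumeration.** Seven items, each zero or non-zero, give 2^7 = 128 patterns. Compared with the 8.2.2.1 flag:

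| Score-specific flag (8.6.3) | Patterns that disagree |
|---|---|
| Total GI > 0 | 0 |
| Abdominal > 0 | 2^3 − 1 = 7 |
| Diarrhea and Loose Stool > 0 | 2^5 − 1 = 31 |

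If nausea is left out of Total GI, the 8.2.2.1 flag still equals that version of Total GI > 0 in every pattern. These are counts of patterns, not of how often each occurs.

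**3. Example.** Gas 1, everything else 0: A = 1/4 = 0.25, D = 0, Total GI > 0. Under 8.2.2.1 the day is symptomatic in all three analyses. Under 8.6.3 it is asymptomatic for Diarrhea and Loose Stool.

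**4. Dilution.** If treatment turns a day with D > 0 into one with D = 0, the 8.2.2.1 count changes only when A and N are also 0 that day. With q the share of such days on which A = N = 0, the fall in the composite count is q times the fall in diarrhea days. The documents give no value for q.

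**5. Size of the mislabeling, under assumptions.** Fifteen simulated settings used rounded 0 to 10 item scores with a day effect common to all items: mean Abdominal score 2.5, 3 or 4 (with Diarrhea 1.5, 2 or 2.5 and nausea 0.7, 1 or 1.2), day-to-day SD 1 to 4, item SD 1 to 2.5. None of these values is in the documents.

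- Composite minus Diarrhea and Loose Stool flag: smallest gap 1.000 − 0.976 = 0.024 of days, largest 0.877 − 0.587 = 0.290. Times 28 days, that is about 0.7 to 8.1 extra days per month.
- Composite minus Abdominal flag: at most 0.877 − 0.860 = 0.017, about 0.5 day per month.

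The rule therefore matters mainly for Diarrhea and Loose Stool.

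**6. Higher cut-offs.** If 2 or 3 replaces 0 inside the same composite rule, there is still one flag per day and three identical analyses. Applied score by score, they need a daily Total GI score. With A = 2, D = 1, N = 0, a sum gives 3 (symptomatic at both cut-offs) and a mean gives 1 (symptomatic at neither). At > 0 the choice makes no difference.

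**The case against.** The strongest reply is that SAP 8.6.3 already states the domain-specific intent: it classifies by score, summarizes by domain and models by domain. Even the opening sentence of the 8.2.2.1 paragraph names the three scores. On that reading the collapse is a programming risk and not what the plan as a whole asks for. This stands as far as intent goes. It does not remove the conflict, because the derivation text gives an explicit rule that produces something else. The very next paragraph of 8.2.2.1, on weekly worst scores, does say that the domains are handled separately. The code in SAP 11.4 contains no derivation that would settle it. The exploratory endpoint wording (SAP 3.3, Protocol 9.4.4) is not readable in the public documents and might help.

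Three stronger readings are tempting, and the documents do not support them.

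- **That the counts sit near their ceiling.** No symptomatic-day rate is given. The run-in criterion (Protocol 5.1, criterion 7) asks for a weekly mean of at least 2.5 in two of four weeks. With seven entries, 7 × 2.5 = 17.5 points can be reached in 2 days at 10 points, so it guarantees only 2 × 2 = 4 of 28 days. The settings in step 5 of the working give 19.6 to 28.0 composite days. A high share is possible, but it would come mainly from the > 0 cut-off: scoring by domain leaves the Total GI flag unchanged and the Abdominal flag nearly so. The cut-offs of 2 and 3 in 8.6.3 partly answer it.
- **That a specific loss of power can be stated.** It would need the variance and within-subject correlation of monthly day counts, and the documents give neither.
- **That a real fall in diarrhea would go unseen in the trial.** Diarrhea is also assessed by the secondary MMRM (SAP 8.6.2.1) and, in SAP 8.6.3, by weekly worst scores, 30% and 50% responders, and BSFS Type 6 or 7 frequency.

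**Conclusion.** The concern holds as a conflict between two SAP sections. That the three sets of counts become identical under 8.2.2.1 is exact for complete diary days and needs no assumption about symptom rates. Dilution of a diarrhea-specific effect also follows from the rule, but its size depends on how often diarrhea occurs without abdominal symptoms or nausea; the figures of 0.7 to 8.1 extra days per month are illustrations under assumed distributions. The scope is narrow: one outcome among the 'Other' efficacy variables, tested without multiplicity adjustment. The primary and secondary analyses do not use the flag. It should still be corrected, because a stated rule gives the wrong variable and the correction is almost free.

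**What to change.** In SAP 8.2.2.1, replace the two sentences that define symptomatic and asymptomatic days with:

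> For each of the Abdominal Symptoms domain, the Diarrhea and Loose Stool domain and the Total GI score separately, a day is symptomatic if that score is >0 and asymptomatic if it is 0. The cut-offs of >=2 and >=3 are applied to that same score.

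Add a definition of the daily Total GI score, for example the mean of its three components, which matches the weekly divide-by-3 formula. State the corresponding daily formula if the version without nausea is also used.

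The cost is a few sentences of SAP text and the matching derivation code, with no new data. Separately, the share of days with a score above 0 can be checked on blinded run-in diaries, to see whether the > 0 cut-off leaves room for change.

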Visit 5 (Week 4/Day 29)

- Chemistry (same tests as screening)
- CBC (same tests as screening)
- HbA1C (subjects with diagnosed Type 1 or Type 2 diabetes only)
- Urinalysis (same tests as screening)
- Stool and urine gluten tests
- Urine pregnancy test (WOCBP only)
- Anti-tTG IgA, anti-DGP IgA
- Serum biomarkers (e.g., IL-15)
- Trough concentration of PRV-015
- ADA

Visit 7 (Week 8/Day 57)

- Chemistry (same tests as screening)
- CBC (same tests as screening)
- Urinalysis (same tests as screening)
- HbA1C (subjects with diagnosed Type 1 or Type 2 diabetes only)
- Stool and urine gluten tests
- Urine pregnancy test (WOCBP only)
- Anti-tTG IgA, anti-DGP IgA
- Serum biomarkers (e.g., IL-15)
- Trough concentration of PRV-015

Visit 9 (Week 12/Day 85)

- Chemistry (same tests as screening)

- CBC (same tests as screening)
- HbA1C (subjects with diagnosed Type 1 or Type 2 diabetes only)
- Urinalysis (same tests as screening)
- Stool and urine gluten tests
- Urine pregnancy test (WOCBP only)
- Anti-tTG IgA, anti-DGP IgA
- Ferritin, iron, TIBC, vitamins D, B12, folate
- Serum biomarkers (e.g., IL-15)
- Trough concentration of PRV-015
- ADA

Visit 11 (Week 16/Day 113)

- Chemistry (same tests as screening)
- CBC (same tests as screening)
- HbA1C (subjects with diagnosed Type 1 or Type 2 diabetes only)
- Urinalysis (same tests as screening)
- Stool and urine gluten tests
- Urine pregnancy test (WOCBP only)
- Anti-tTG IgA, anti-DGP IgA
- Serum biomarkers (e.g., IL-15)
- Trough concentration of PRV-015

Visit 13 (Week 20/Day 141)

- Chemistry (same tests as screening)
- CBC (same tests as screening)
- HbA1C (subjects with diagnosed Type 1 or Type 2 diabetes only)
- Urinalysis (same tests as screening)
- Stool and urine gluten tests
- Urine pregnancy test (WOCBP only)
- Anti-tTG IgA, anti-DGP IgA
- Serum biomarkers (e.g., IL-15)
- Trough concentration of PRV-015

Visit 14 (Week 22/Day 155)

- Trough concentration of PRV-015
- ADA

Visit 15 (Week 24/Day 169) or Early Termination

- Chemistry (same tests as screening)
- CBC (same tests as screening)
- HbA1C (subjects with diagnosed Type 1 or Type 2 diabetes only)
- Urinalysis (same tests as screening)
- Stool and urine gluten tests

- Urine pregnancy test (WOCBP only)
- Anti-tTG IgA, anti-DGP IgA
- Ferritin, iron, TIBC, vitamins D, B12, folate
- Serum biomarkers (e.g., IL-15)
- Trough concentration of PRV-015
- ADA

Visit 16 (Week 28/Day 197)

- Chemistry (same tests as screening)
- CBC (same tests as screening)

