PROACTIVE Dietary Questionnaire	Most recent assessment prior to the first administration of double-blind treatment.				

Visit Windowing (post-baseline) for Patient-Reported Assessments captured in eDiary

Analysis visit windows will be applied for following patient-reported eDiary assessments for postbaseline visits and are described below:

- CeD PRO
- BSFS
- PGIS/PGIC
- Weekly Diet Questionnaire

CeD PRO analysis visit windows (for week-based analysis).

In case of missing visit, the prior visit + 14 days will be taken.

Period	Analysis Visit	Days included in analysis window
Double-blind treatment	Week 2	Days -7 to -1 prior to actual Visit 4 date
Double-blind treatment	Week 4	Days -7 to -1 prior to actual Visit 5 date
Double-blind treatment	Week 6	Days -7 to -1 prior to actual Visit 6 date
Double-blind treatment	Week 8	Days -7 to -1 prior to actual Visit 7 date
Double-blind treatment	Week 10	Days -7 to -1 prior to actual Visit 8 date
Double-blind treatment	Week 12	Days -7 to -1 prior to actual Visit 9 date
Double-blind treatment	Week 14	Days -7 to -1 prior to actual Visit 10 date
Double-blind treatment	Week 16	Days -7 to -1 prior to actual Visit 11 date
Double-blind treatment	Week 18	Days -7 to -1 prior to actual Visit 12 date
Double-blind treatment	Week 20	Days -7 to -1 prior to actual Visit 13 date
Double-blind treatment	Week 22	Days -7 to -1 prior to actual Visit 14 date
Double-blind treatment	Week 24	Days -7 to -1 prior to actual Visit 15 date

CeD PRO analysis visit windows (for month-based analysis of symptomatic days)

Period	Month	Days included in analysis window
Run-in	Baseline	Days -28 to -1 prior to Actual Visit 3 date
Double-blind treatment	1	Actual Visit 3 date (inclusive) through day prior to actual Visit 5 date if available, or Visit 3 date + 28 days (if Visit 5 is missing)
Double-blind treatment	2	Actual Visit 5 date (inclusive) through day prior to actual Visit 7 date if available, or Visit 5 date + 28 days (if Visit 7 is missing) or Visit 7 – 28 days if Visit 5 is missing
Double-blind treatment 3		Actual Visit 7 date (inclusive) through day prior to actual Visit 9 date if available, or Visit 7 date + 28 days (if Visit 9 is missing) or Visit 9 – 28 days if Visit 7 is missing
Double-blind treatment	4	Actual Visit 9 date (inclusive) through day prior to actual Visit 11 date if available, or Visit 9 date + 28 days (if Visit 11 is missing) or Visit 11 -28 days if Visit 9 is missing

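### In the symptomatic-day month windows a missing bounding visit gets two different dates, so adjacent months can overlap or leave a gap, and a month with both bounding visits missing has no window

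*SAP*

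**What the plan says.** The month-based table in SAP 8.2.2.1 sets a baseline month, "Days -28 to -1 prior to Actual Visit 3 date", and six treatment months. Month 1 begins at "Actual Visit 3 date (inclusive") and runs "through day prior to actual Visit 5 date if available, or Visit 3 date + 28 days (if Visit 5 is missing"). Month 2 runs from Visit 5 to the day before Visit 7, with two fallbacks: "or Visit 5 date + 28 days (if Visit 7 is missing) or Visit 7 – 28 days if Visit 5 is missing". Months 3 to 6 repeat the Month 2 pattern with Visits 7, 9, 11, 13 and 15.

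The week-based CeD PRO table in the same section has its own missing-visit rule: "In case of missing visit, the prior visit + 14 days will be taken". It is repeated for the BSFS windows but not for the month table. No clause covers a month whose opening and closing visits are both missing.

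SAP 8.6.3 uses the monthly counts in two ways. It summarizes the ratio of symptomatic days to days in the month, and it fits an MMRM to change from baseline in the monthly totals.

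**The concern.** A boundary between two months should be one date. Here a missing boundary is dated forward from the earlier visit to close one month, and backward from the later visit to open the next. The two dates agree only for one particular spacing of the neighbouring visits; otherwise some diary days fall in both months or in neither. When two consecutive bounding visits are missing, the month between them cannot be built at all.

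This can arise in practice. The CeD PRO is a daily home eDiary that runs to Visit 16, so diaries can exist when a site visit does not. The interior boundaries (Visits 5, 7, 9, 11 and 13) are not among the visits that may be done remotely (6, 8, 10 and 12). At stake is the count that enters the MMRM for affected subjects, and whether the programmer must choose between readings and invent a rule for an undefined month.

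**Working it through.** **Inputs.** The bounding visits fall on Days 1, 29, 57, 85, 113, 141 and 169, with ±2 days from Visit 4 onward (Schedule of Activities; Protocol 8.1 also gives "Visit 5 (Week 4/Day 29")). The fallbacks are those in the SAP month table.

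**No visit missing, all on schedule.** The months are Days 1–28, 29–56, 57–84, 85–112, 113–140 and 141–168: six months of 28 days, 168 in all, with no overlap or gap. This matches the 28-day baseline month.

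**One visit missing.** Let A and B be the attended visits on either side of it, and D = B − A. The next month opens on B − 28. The earlier month closes on:

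- A + 28 on the literal wording. Days counted twice = (A + 28) − (B − 28) + 1 = 57 − D; if negative, that many days are lost.
- A + 27 if the day-before qualifier also governs the substitute date. Days counted twice = 56 − D; if negative, that many days are lost.

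With Visit 5 missing, A = Visit 3 (Day 1) and B = Visit 7:

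| Visit 7 day | D | Literal: twice / lost | Qualifier carried over: twice / lost |
|---|---|---|---|
| 55 | 54 | 3 / 0 | 2 / 0 |
| 56 | 55 | 2 / 0 | 1 / 0 |
| 57 | 56 | 1 / 0 | 0 / 0 |
| 58 | 57 | 0 / 0 | 0 / 1 |
| 59 | 58 | 0 / 1 | 0 / 2 |

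On the literal wording Month 1 is Days 1–29, which is 29 days, and Day 29 is duplicated even when Visit 7 is on schedule. Three days are 3/28 = 10.7% of a nominal month; one day is 3.6%.

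If Visit 7 is the missing one, Visits 5 and 9 can each move by 2 days, so D runs from 52 to 60. The extremes are then 5 days twice or 3 lost (literal), and 4 twice or 4 lost (qualifier carried over).

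**Two consecutive bounding visits missing**, for example Visits 7 and 9, others on schedule. Month 2 closes on Day 57 (literal) or Day 56. Month 4 opens on 113 − 28 = Day 85. Month 3 has no window. The lost days are 58–84, which is 27 days (literal), or 57–84, which is 28 days.

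The weekly rule, with Visit 8 attended on Day 71, still uses Days 64–70 (Week 10) and Days 78–84 (Week 12, from 71 + 14 = 85). That is 14 days, about half of those lost from the monthly count.

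**Single carry-forward rule.** With Visit 5 missing, the boundary is Day 29 for both months.

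- Visit 7 on Day 55: Month 2 = Days 29–54 (26 days), Month 3 = Days 55–84 (30 days).
- Visit 7 on Day 59: Month 2 = Days 29–58 (30 days), Month 3 = Days 59–84 (26 days).
- Visits 7 and 9 both missing: Month 3 = Days 57–84 (28 days).

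In every case 0 days are counted twice and 0 are lost.

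**The case against.** The best reply is that the substitute date stands in for the missing visit, so the day-before qualifier applies to it too. The month is then 28 days, matches baseline, and meets the next month exactly when visits are on schedule. That reading is natural, and the 29-day month should not be asserted as the SAP's certain meaning. It does not remove the overlap or gap for off-schedule visits, nor the undefined month.

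Second, month length varies even with no visit missed: 26 to 30 days for Month 1 and 24 to 32 for later months, given the ±2-day windows. The descriptive ratios divide by days in the month and so absorb unequal length. Both points stand. A longer or shorter month is therefore not the distinctive defect. The distinctive defects are days assigned to two months or to none, and the MMRM on raw totals has no correction for them.

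Third, an undefined month needs two consecutive odd-numbered visits to be missed while the diary continues. That is 5 of the 15 possible pairs among Visits 5 to 15; missing Visits 5 and 9, for example, does not do it. The documents give no rate of missed visits.

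A reader might also infer three stronger things that the documents do not support:

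- **That the 24-week totals are wrong.** SAP 8.2.2.1 lists the treatment-period total alongside the monthly counts and does not say it is summed from them. A direct diary count would be unaffected.
- **That the treatment comparison is biased.** Nothing in the documents indicates that missed visits differ by arm.
- **That the primary result is touched.** It rests on the weekly windows.

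**Conclusion.** The month rule is defective as written, but the consequence is small. Under either reading, adjacent months can overlap or leave a gap when the visits around a missing one are off schedule. For a missing Visit 5 with Visit 7 in window, this reaches 3 days twice or 1 lost on the literal wording, and 2 twice or 2 lost otherwise. The literal wording also gives a 29-day month with one duplicated day when visits are on schedule. A month with both bounding visits missing has no window, at a cost of 27 or 28 diary days.

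These figures assume visits within ±2 days, other visits as stated, and a diary that continues through the missed visit. The effect is confined to the exploratory MMRM on monthly totals, for subjects who missed a bounding visit. It extends to the 24-week total only if that is summed from the months. This is worth correcting but would not change the trial's main conclusions.

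**What to change.** In SAP 8.2.2.1, delete the plus-28 and minus-28 clauses for Months 1 to 6 and state one rule: a missing bounding visit takes the previous bounding date (actual or imputed) plus 28 days, and each month runs from its bounding date through the day before the next bounding date, for as long as the diary continues.

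Months are then contiguous and do not overlap, and the rule follows the same forward logic as the weekly windows. It does not equalize month lengths, which still vary with visit timing, and it sets no minimum number of completed diary days per month; the existing four-day minimum applies to weekly scores only.

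The cost is one sentence in the SAP and a small change to the derivation program. No endpoint, model or study procedure changes.
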